The United States Food and Drug Administration (FDA) has approved a dose of 100 units of Botox® for refractory OAB based on rates of improvement of continence episodes while weighing adverse events [the most common being urinary tract infections (UTIs) and urinary retention requiring clean intermittent catheterization (CIC)]. However, what is not known is the optimal number of injections of the 100 units. The AUA/SUFU OAB guidelines do not recommend a specific number of injection sites. The European Association of Urology consensus report [3] recommends 10 Units/ml per injection (10 one ml injections for 100 units). However, this was not based on randomized trials, and no studies have been done that directly compare different numbers of injection sites. The package insert for Botox® recommends 100 units combined with 10 cc of saline to be distributed in 20 injections (0.5 cc per injection) [4]. However, a literature search involving the methods of administration shows a range of 10 - 30 injections for 100 units of Botox® [3,5,11].

One of the concerns about administering Botox® into the bladder is the patient's comfort during the procedure as he or she is usually awake during this office based procedure. Patient experience is becoming a more important aspect of patient care, and is a marker for which provider are being measured. Currently, there are ongoing studies to assess whether or not 10 injections of Botox delivers the equivalent efficacy of 20 injections of Botox in a national, multi-institutional trial. Uniquely, we would like to assess if there is a difference in the pain of procedure with 10 injections versus 20 injections.

Our hypothesis is that Botox® distributed in 10 injections will result less pain of procedure perceived by the patient compared to the pain perceived by the patients receiving 20 injections.

Objectives:

• **Primary endpoint:** The primary endpoint to be assessed is the difference in pain of procedure experienced by those receiving 100 units of Botox ® in 10 injections versus those receiving 100 units of Botox in 20 injections. Our hypothesis is that those receiving 10 injections will perceive less pain.

- Pain of procedure:
 - Pain of procedure: To assess pain of procedure, we will use the 11 point Numeric Pain Rating Scale (NPRS). We expect that the patients receiving 10 injections will have less pain associated with the procedure. The patients will rate their level of pain immediately following the completion of bladder injections by selecting a whole number from 0 to 10 that represents their level of pain (0 is no pain at all and 10 is the most severe pain) during the procedure. This scale has been validated, and correlates similarly to other pain scales [7].
- Secondary endpoints: Secondary endpoints to be assessed will be efficacy, OAB symptoms (nocturia, urgency, and frequency), post void residual volume (PVR) at 2 weeks and 12 week post-procedure, disease specific bother, health related quality of life (HRQoL), the patient's perceptions of change, and adverse events as detailed below:
 - Efficacy: The reduction in mean urge incontinence episodes which will be calculated by averaging the amount of urge urinary incontinence episodes over 3 days as recorded in a bladder diary. Success will be defined as a greater than 50% reduction in urge incontinence episodes after intradetrusor Botox® based on 3-day bladder diaries collected at baseline and 12 weeks post-injection. This outcome measure is consistent with results reported in previous trials involving Botox® for overactive bladder [6].
 - Disease specific bother and HRQoL: To assess OAB symptoms other than incontinence and impact on quality of life, we will administer the Overactive Bladder Questionnaire Short Form (OABq-SF) at baseline, at 2 weeks, and at 12 weeks post-procedure. This is an abbreviated version of the Overactive Bladder Questionnaire (OABq) developed to evaluate the bother and health related quality of life for patients with overactive bladder. The OAB-SF contains 6 items to assess symptom bother and 13 items to assess HRQOL. This questionnaire is commonly used, and has been validated for use in clinical practice [8].
 - PVR at 2 weeks and 12 weeks: To measure PVR at 2 weeks and 12 weeks, we will use a bladder scanner which measures volume based on ultrasound. The provider may also chose to measure PVR by straight catheterization at his or her discretion.
 - Patient's Global Impression of Change (PGIC) scale: In order to help determine the clinical significance of change, we will utilize the PGIC scale [16] administered at 2 weeks and 12 weeks post-injection.

Adverse events: Specific to intradetrusor injections of Botox®, the most common adverse events are urinary retention requiring intermittent catheterization (approximately 4%) [9] and urinary tract infections (approximately 15.5%-35%) [10]. Patients will be closely monitored for urinary tract infections as they will undergo urinanalysis and assessment of symptoms at their post-operative visits.

Methods and Measures

- Design:
 - This study is a randomized clinical trial to assess whether or not 10 injections of 100 units of intradetrusor Botox® toxin is perceived as less painful compared to 20 injections of 100 units of intradetrusor Botox® toxin for the treatment of refractory OAB. Refractory OAB is defined as persistent urinary frequency and urgency despite behavioral modifications, failing a trial of 2 medications (anticholinergics or beta 3 agonists), have a contraindication to the medications, or are unable to tolerate medications due to allergies or side effects.
 - The primary outcome will be assessed by the patient completing the pain of procedure questionnaire, the NPRS, to be completed by the patient immediately after the procedure. The patient will receive the questionnaire from the nurse or medical assistant after the provider has performed the procedure. We will then compare mean value of the NPRS for the 10 injection group to the 20 injection group.
 - Efficacy will be assessed by comparing study participant's reduction in urge urinary incontinence episodes based on a 3 day voiding diary to be shared by the participant at baseline and 12 weeks post-procedure. This diary is dispensed to all patients during their visit prior to procedure visit as a part of standard of care. If subjects demonstrate a 50% reduction in urge incontinence episodes on a 3-day bladder diary, they will be categorized as "treatment success" whereas those who do not will be categorized as "treatment failure." This dichotomous outcome will define efficacy as a secondary endpoint.
 - All eligible participants will be considered for the study. Patients will be counseled about the study in the office setting. Upon enrollment, patients will share a 3-day voiding diary. Diary is dispensed to all patients when they decide to undergo injection procedure. Disease specific bother and health related quality of life questionnaires will be completed following consenting. As per standard of care, urinalysis and post-void residual volume will be measurement. The only assessment in this list that is not part of standard clinical care are the questionnaires. If patients are on medications for

overactive bladder, they will be required to stop at least 3 weeks prior to undergoing the baseline 3 day voiding diary.

After consenting to enrollment in the study, the patients will be scheduled for Botox® injections in the office. Randomization will be performed using random sequence number generation in blocks of 10 with randomization assignment concealed in sequentially numbered opaque envelopes. Randomization will be performed before the study startup by the coordinator using online available tool (sealed envelope). Envelopes with 50% carrying 10 injections instructions, and 50% carrying 20 injections instructions are prepared in advance, sealed, numbered 1 to 50, and stored in a locked cabinet at the Urology clinic at [name]. Three envelopes will be carried to the Greensboro Wake Health System during coordinator's scheduled clinic days. And then coordinator will bring those packets back to the [name] Urology clinic on a regular base. On the day of the procedure, the provider will select the next numbered envelope that will contain the randomization assignment for the number of injections. Subjects will be blinded to the randomization result. All patients will undergo a urinalysis prior to the procedure. If there is concern for an acute, untreated urinary tract infection, the patient does not undergo the procedure, and is treated with antibiotics while a urine culture is sent. All participants will be given preoperative antibiotics (except aminoglycosides). 100 units of Botox® will be combined with 20 cc saline for the purposes of 20 injections, or 100 units of Botox® will be combined with 10 cc of sterile saline for the purpose of 10 injections. Lidocaine Jelly locally. And the bladder will be instilled with 30ml of Marcaine and 5ml of NaHCo3 solution through a catheter for at least 15 minutes prior to the procedure. Cystoscopy with either a rigid or flexible cystoscope (per surgeon preference) will be performed using sterile technique. The Botox® will be injected in a grid like pattern avoiding the trigone as seen below. Study patients do not know the number of injections received in the bladder. There are two providers in the room for each procedure. Injection counting will be verbalized as Injection 1, Injection 2... to up to Injection 20 by non-injecting provider. A patient and a provider who is injecting will hear total of 20 counts. Providers will know the randomization prior to procedure, and a decision will be cleared between two providers whether to account pseudo injection at odd or even number for patients receiving 10 injections. A patient randomized to 10 injections will receive 10 injections at alternate count. All patients will be informed in advance about the procedure at the time of consenting. The patient will be allowed to void on her own postprocedure. Immediately after the procedure, the patient will receive a questionnaire to rate the pain of procedure using the numeric pain scale. The patient will then be discharged to home. Figure 1: Diagram showing sites of injections for patients undergoing 10 injections of 100 units of Botox®.

Figure 1: Diagram showing sites of injections for patients undergoing 10 injections of 100 units of Botox®.

[figure not shown]

Figure 2: Diagram showing sites of injections for patients undergoing 20 injections of 100 units of Botox®

- At two weeks, the patient will return to clinic for a standard office visit. She will have a post void residual checked using either a bladder scan or catheter, and a urinalysis (urine culture will be sent per clinic protocol). If a urine culture grows any bacteria, and the patient is symptomatic, she will be treated with culture specific antibiotics. She will then be asked about symptoms of a urinary tract infection, if they have been treated for a urinary tract infection, difficulty emptying the bladder, or required intermittent or an

indwelling Foley catheter since the Botox® therapy. Subjects will complete the PGI-C and the OAB-SF. The patient will be sent home with a 3-day bladder diary to complete just prior to the 12-week visit.

- At 12 weeks, the patient will return to clinic and her 3-day bladder diary will be reviewed. A post void residual volume will be checked using either a bladder scan or catheter, and a urinalysis will be sent per standard practice (urine culture will be sent per clinic protocol). If a urine culture grows any amount of bacteria and the patient is symptomatic, she will be treated with culture specific antibiotics. She will then be asked about symptoms of a urinary tract infection, if they have been treated for a urinary tract infection, difficulty emptying her bladder, or required intermittent or an indwelling Foley catheter since the Botox® therapy. She will again take the OABq-SF and PGIC.
- Setting:
 - This study will take place at two Urology clinic locations at Wake Forest Baptist Medical Center, [name] in Winston Salem, NC and [name] in Greensboro, NC.

Subjects Selection Criteria

- Inclusion criteria: Subjects must meet the following inclusion criteria in order to be eligible for the study
 - 1. Female gender
 - 2. At least 18 years of age
 - 3. Have already decided to undergo intradetrusor Botox® injections for treatment of refractory overactive bladder.
 - 4. Able and willing to learn clean intermittent catheterization (or care provider is willing and able to perform intermittent catheterization).
 - 5. Understands and is willing to undergo follow up and complete questionnaires as described in this protocol
 - 6. Able to give informed consent
- Exclusion Criteria:
 - 1. Male gender
 - 2. Neurological conditions (Examples: Cerebral vascular accident within 6 months prior to treatment, Parkinson's disease, Multiple Sclerosis, and Spina Bifida).
 - 3. Acute urinary tract infection
 - 4. Treatment with Botox® toxin for other conditions
 - 5. Allergy to Botox® toxin
 - 6. Hematuria that has not been worked up
 - 7. Known bladder malignancy

- 8. Previous history of bladder augmentation
- 9. Currently pregnant (with no plans to become pregnant within 6 months of enrollment) or breastfeeding
- 10. Currently taking aminoglycoside antibiotics
- 11.PVR >150 cc (measured by bladder scan or by catheterization) prior to enrollment
- 12. History of bladder pain syndrome.
- Sample Size:
 - This study is unique as there are no previous trials assessing pain of procedure associated with intravesical administration of bladder Botox. To calculate sample size in the study, we will assume an effect of size of 1. We expect that patients receiving 20 injections will be within the moderate pain range (between 5 to 7 on the NPR scale). Therefor we will assume a mean NPR rating for patients receiving 20 injections would be 6 with a standard deviation of 2. Patients receiving 10 injections will be expected to have less pain and be in the mild pain range (from 1 to 4 on the NPR scale). Based on this, we would need 16 patients in each group. Accounting for a 20% drop out rate, we would need to accrue 20 patients in each group.

• Statistical Analysis:

- 1. Primary endpoint: Each patient will be asked to rate her pain level of procedure by completing the NPRS immediately after her procedure. The mean NPRS score of each group (10 injections vs 20 injections) will be calculated and compared using a paired T test.
- 2. Secondary endpoints
 - Each patient's mean number of urge urinary incontinence episodes will be calculated by averaging the number of urge urinary incontinence episodes collected over 3 days as recorded on a bladder diary. This will be calculated pre-intervention at baseline and at 12 weeks. As previously described, "treatment success" is defined achieving greater than 50% reduction in the number of urge urinary incontinence episodes at 12 weeks after treatment with Botox®. A "treatment failure" will be defined as achieving less than 50% reduction in the number of urge urinary incontinence episodes at 12 weeks after treatment with Botox®. A "treatment failure" will be defined as achieving less than 50% reduction in the number of urge urinary incontinence episodes at 12 weeks after treatment with Botox®. Our hypothesis is that there will be more significantly "treatment responders" in patients receiving 20 injections compared to 10 injections. To assess for clinical significance Chi square (X²) will be used.

- OABq-SF and PGIC collected from the group receiving 20 injections and the group receiving 10 injections. The mean will be calculated for each of the outcomes and for each of the groups. The result will be compared using paired t-test.
- We will compare the mean number of patients with urinary retention and UTIs in patients in both groups (those receiving 20 injections and those receiving 10 injections). To test for significance we will use the t-test.

Interventions and Interactions

- This study will use the FDA approved dose for refractory overactive bladder which is 100 units of onabotulinum toxin A (Botox®).
- Per surgeon preference, a flexible cystoscope or a rigid cystoscope will be used to inject the Botox® in the wall of the bladder.
- Injections will be in a grid-like fashion.
- We will use a 3 day bladder diary obtained from the International Urogynecological Association (IUGA) for baseline and 12 week follow up. (Appendix 1)
- Immediately after the treatment, patients will be asked to rate their pain using the Numeric Pain Scale. Please see appendix.
- Patients will be assessed for adverse events, symptom specific and global quality of life using the form in the appendix.
- All surveys will be handed to the patients by nursing. Patients will fill out the forms before seeing a physician.

Outcome Measures: Outcome measures to be assessed include: pain of procedure, urge urinary incontinence episodes, efficacy, bother, HRQoL, PGIC, urinary tract infection, urinary retention requiring catheterization.

Calendar of Events:

		Day of Procedure (Botox		
Form/Intervention	Baseline	Injections)	2 weeks	12 weeks
ICF	х			
PVR	х		х	х
Urinalysis	х	Х	х	х
Study Inclusion Form	х			
Bladder Diary	х	*		х
Randomization		Х		
Pain Scale		Х		
OABq-SF	х		х	х
PGIC			х	х
Adverse Events Questionnare			х	x
Completion of Study Form				x

*: Collect the completed Diary

Human Subjections Projection

Subject Recruitment Methods: Patients evaluated in the office setting and who are diagnosed with refractory overactive bladder will be counseled regarding their options for treatment. The 3 treatment options include: intradetrusor injection of onabotulinum toxin, sacral neuromodulation, and percutaneous tibial nerve stimulation. After weighing the risks and benefits of all procedures, patients opting for therapy with onabotulinum toxin A will be considered for the trial. A member of the study team will discuss eligibility, review the inclusion/exclusion criteria, and answer questions. Informed consent will be signed. Three day diary provided during the at visit as per Standard of Care will be reviewed belonging all participants in order to capture the information. Any patient who wishes to withdraw from the study may do so at any time. If the patient chooses to withdraw, they will be presented with the option to allow the data collected up to that point to be retained, or have it removed.

Protocol version: 1 Page 11 of 21

All data will be kept on a secure password protected and encrypted hospital issued computers and contained within password protected files. Source documents will be kept in a locked drawer on Wake Forest Baptist Health property.

Informed Consent: Signed informed consent will be obtained from each subject. The principal investigator and co-investigators will obtain informed consent. The informed consent process will take place in the Urology offices in either Winston-Salem, NC or Greensboro, NC.

Confidentiality and Privacy: Confidentiality will be protected by collecting only the information needed to assess study outcomes, minimizing the collection of any information to the fullest extent possible that could directly identify subjects, and maintaining all study information in a secure manner. To help ensure subject privacy and confidentiality, only a unique study identifier will appear on the data collection form. Any collected patient identifying information corresponding to the unique study identifier will be maintained on a linkage file, stored separately from the data. The linkage file will be kept secure, with access limited to designated study personnel. Following data collection, subject identifying information will be destroyed 3 years after closure of the study by shredding, consistent with data validation and study design, producing an anonymous analytical data set. Data access will be limited to study staff. Data and records will be kept locked and secured, with any computer data password protected. No reference to any individual participant will appear in reports, presentations, or publications that may arise from the study.

Data and Safety Monitoring: The principal investigator will be responsible for the overall monitoring of the data and safety of study participants. The principal investigator will be assisted by other members of the study staff.

Reporting of Unanticipated Problems, Adverse Events or Deviations: Any unanticipated issues, serious and unexpected adverse events, deviations or protocol changes will be promptly reported to the principal investigator or member of the research team, the IRB, sponsor, and appropriate government agency if appropriate.

Bladder Diary Sample

This simple chart allows you to record the fluid you drink and the urine you pass over 3 days (not necessarily consecutive) in the week prior to your clinic appointment. This can provide valuable information.

Please fill in approximately when and how much fluid you drink and the type of liquid.

Please fill in the time and amount (in mls, or ounces) of urine passed, and mark with a star if you have leaked or mark with a "P" if you have needed to change your pad.

Here is an example of a filled chart to help you complete your own more easily.

Date/Time DD.MM.YY	Liquid Intake (ml)	Volume of Urine (ml)	Leaks	Pad Change
21.02.06			*	
0215		150		
0715		250		
0800	1 cup of coffee		þ.	
0820		60	*	Р
0930	Cup orange juice		*	
1000		100		
1200	2 mugs coffee			
1400		300		
1430		20		
1530	Cup of tea 200ml	200		
1600				
1800	Cup of tea 200ml		*	Р
1900		100	*	
2000	Glass beer 200ml	20		
2030	Glass wine 50ml		*	
2200				Р
2300		150		

IUGA Office | [contact] | www.iuga.org

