Appendix 2: Pain assessment to be completed immediately after the procedure

	Medical Record Number:		
	Date:		
1	Since your last visit, have you been diagnosed with a UTI?	Yes	No
2	Do you have any of the following symptoms?		
3	- Burning with urination	Yes	No
4	- Blood in the urine	Yes	No
5	- Fever	Yes	No
6	Since your last visit, have you been evaluated in the emergency room?	Yes	No
7	Since your last visit, have you been evaluated by your primary doctor?	Yes	No
8	Since your last visit, have you required a urinary catheter, (intermittent or indwelling)?	Yes	No
9	Since your last visit, have you seen blood in your urine that lasted more than 48 hr.?	Yes	No
10	Since your last visit, have you had difficulty swallowing?	Yes	No
11	Since your last visit, have you had difficulty breathing?	Yes	No

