Official Title: A Randomized Clinical Trial of 100 Units of Intradetrusor Onabotulinum Toxin A for Refractory Overactive Bladder - Is 10 Injections Less Painful Than 20 Injections?

NCT04124939 Date: 7/31/23

Statistical Analysis - 10 vs 20 Botox Injections

Standard descriptive statistics were used to compare demographic and clinical characteristics. Frequency and percentages were reported for categorical data. Chi-square and fisher exact test for categorical variables and student t-test or Mann-Whitney U test for continuous variables were used to assess significant differences between the groups. Statistical analysis was performed on R Software.

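### Post-void residual volume is a named secondary endpoint with no analysis of its own, and the generic SAP test leaves the baseline measurement unused

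*Protocol*

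**What the plan says.** The secondary endpoints in the protocol's Objectives include "post void residual volume (PVR) at 2 weeks and 12 week post-procedure". The sub-item for this endpoint covers measurement only: a bladder scanner is used, and "The provider may also chose to measure PVR by straight catheterization at his or her discretion".

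Baseline values exist. The Design section says "As per standard of care, urinalysis and post-void residual volume will be measurement" at enrolment, and the Calendar of Events schedules the measurement at baseline, 2 weeks and 12 weeks. The baseline value also decides eligibility, since exclusion criterion 11 is "PVR >150 cc (measured by bladder scan or by catheterization) prior to enrollment".

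The protocol's Statistical Analysis section covers the pain score, incontinence treatment success, the OABq-SF and PGIC, and the numbers of women with retention and with urinary tract infection. It gives residual volume no summary measure, contrast or test. The Outcome Measures paragraph omits it too: "Outcome measures to be assessed include: pain of procedure, urge urinary incontinence episodes, efficacy, bother, HRQoL, PGIC, urinary tract infection, urinary retention requiring catheterization".

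The SAP is a single paragraph. The part that could apply is "student t-test or Mann-Whitney U test for continuous variables were used to assess significant differences between the groups".

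**The concern.** An endpoint that is declared and measured three times should have a stated analysis. Here the analyst must choose between the raw follow-up value and the change from baseline, between the t-test and the rank test, and between visits (or both). Nothing in the documents fixes these choices before the data are seen.

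The second cost is precision. In a randomised comparison of a continuous measure, a baseline value of the same measure is usually the most useful covariate. This trial collects it and, as written, uses it only to screen women. With 16 to 20 women per arm, a comparison of this endpoint is imprecise to begin with.

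**Working it through.** **1. The plan's own figure.** The Sample Size section gives 16 per group for the pain score. Inputs: SD 2 and effect size 1, read as a 2-point difference. Two-sided alpha of 0.05 and 80% power are not stated and are assumed here.

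n = 2 × [(1.960 + 0.842) × 2 / 2]² = 15.7, rounded up to 16. With 20% dropout, 16 / 0.80 = 20.

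The figure reproduces, but it concerns pain. The documents give no SD, difference or correlation for residual volume, so the results below are in SD units with an assumed correlation r.

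**2. Where the endpoint appears.**

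| Place | Residual volume mentioned? |
|---|---|
| Protocol, Objectives (secondary endpoints) | Yes, at 2 and 12 weeks |
| Protocol, Calendar of Events | Yes, at baseline, 2 and 12 weeks |
| Protocol, exclusion criterion 11 | Yes, as a ceiling of 150 cc |
| Protocol, Statistical Analysis | No |
| Protocol, Outcome Measures list | No |
| SAP | Not by name; only as a continuous variable |

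**3. What baseline adjustment buys.** Relative to the unadjusted follow-up comparison, ANCOVA multiplies the variance by 1 − r² and the standard error by √(1 − r²). A change score, with equal SDs at both times, multiplies the variance by 2(1 − r). The equivalent gain in sample size from ANCOVA is 1/(1 − r²). The last column is the difference detectable with 80% power at two-sided 0.05 (noncentral t, 2n − 3 degrees of freedom for ANCOVA) with 20 per arm.

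| r (assumed) | ANCOVA variance | ANCOVA SE | Equivalent sample size | Change-score variance | Detectable difference, 20 per arm |
|---|---|---|---|---|---|
| Unadjusted | 1.00 | 1.00 | 1.00 | – | 0.91 SD |
| 0.3 | 0.91 | 0.954 | 1.10 | 1.40 | 0.87 SD |
| 0.5 | 0.75 | 0.866 | 1.33 | 1.00 | 0.79 SD |
| 0.6 | 0.64 | 0.800 | 1.56 | 0.80 | 0.73 SD |

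With 16 per arm the detectable difference is 1.02 SD unadjusted, and 0.98, 0.89 and 0.82 SD at r = 0.3, 0.5 and 0.6.

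The standard error therefore falls by about 5% (r = 0.3) to 20% (r = 0.6). The 150 cc ceiling restricts the baseline range, which tends to lower r and so points to the lower end. A low r also makes the change score a poor substitute: below r = 0.5 it is less precise than ignoring baseline altogether.

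**4. Women who need a catheter.** The protocol's Adverse events paragraph cites retention needing catheterization at about 4%. With 40 women, 0.04 × 40 = 1.6 are expected, and the chance of at least one is 1 − 0.96⁴⁰ = 80%. With 32 women the figures are 1.3 and 1 − 0.96³² = 73%.

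The documents do not say what value such a woman contributes. One woman can move a raw mean. If her volume is R and the others in an arm of n average m, leaving her out shifts the arm mean by (R − m)/n. With n = 16 and assumed values, (200 − 50)/16 = 9 mL and (400 − 30)/16 = 23 mL. That is reason to state the handling and show its influence. It does not show that any woman will be left out.

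**The case against.** The strongest reply is that an analysis does exist. Residual volume is continuous, the SAP names tests for continuous variables, and nothing there forbids a change score. Randomisation makes the unadjusted comparison unbiased. The endpoint is secondary, the sample size was set for pain, and the likely gain is small: at r = 0.3 the detectable difference with 20 per arm moves only from 0.91 to 0.87 SD. All of this stands. It limits the point to specification and efficiency, and it leaves the pain result untouched. It does not supply the missing choice of measure and visit, nor a reason to leave the baseline value unused.

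A reader might go further and infer that women catheterising for retention drop out of the comparison or enter with falsely low volumes, so that the plan hides a difference between arms. The documents do not support this. They give no rule for dropping these women or scoring them low, and the visit descriptions call for the measurement by scan or catheter without exception. The Statistical Analysis section compares retention between the arms separately, so these women are counted. A large loss of power on this ground would need catheter rates about three times the cited 4%.

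Nor do the documents support worst rank as the main analysis. Item 8 of the follow-up adverse event questionnaire (Appendix 3) asks about catheter use since the last visit, so a woman who has recovered by week 12 can still answer yes.

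**Conclusion.** The point holds as a gap in specification plus a free gain in precision. A named secondary endpoint is missing from the protocol's analysis section and outcome list, and the generic SAP test leaves its baseline value unused. Adjustment would cut the standard error by 5% to 20%, equivalent to 10% to 56% more women. That range rests wholly on an assumed correlation of 0.3 to 0.6, and the lower end is the more likely. The primary endpoint and the sample size are unaffected. The handling of women who needed a catheter should be stated, but no bias from it can be established from the documents.

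**What to change.** Add residual volume at 2 and 12 weeks to the protocol's Statistical Analysis section, its Outcome Measures list and the SAP.

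- **Main analysis:** compare the arms at week 2 and at week 12 by ANCOVA on log(PVR+1) with baseline residual volume as covariate. Use rank ANCOVA if the logged values are still skewed. Report the adjusted difference, which is a ratio on the log scale, with a 95% confidence interval. The rank version does not give a difference in mL, and the report should say so if it is used.
- **Sensitivity analysis only:** repeat the rank version with women recorded as needing a catheter (Appendix 3, item 8) given the worst rank. State that the item covers the period since the last visit and not current use. The log version cannot take a worst rank without an arbitrary volume.

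The cost is a few sentences of text and a few lines of R, with no new data. The SAP is dated 7/31/23 and written in the past tense, so the analysis may already be done. In that case, re-run it on the collected data and label it post hoc.
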